## 5. Clinical and Laboratory Methods

Timing of each study procedure is provided in Table 4 found in Appendix B. No equipment for these tests is being used to diagnose, cure, mitigate, treat, or prevent a disease or condition in this protocol.

During the study, no exercise interventions will be offered by Department of Rehabilitation Medicine unless felt to be important for patient safety. Patients may continue an exercise regimen that they have been on prior to the trial initiation, although certain activities may be restricted at the time of specific assessments.

**Abbreviated Title:** Sodium Thiosulfate (STIC)

**Version Date:** July 07, 2023

## **5.1. Medical History**

A full, thorough medical history will be obtained from all participants and/or their parents at the screening visit and at week -10 visit. No medical history will be taken at Week -4 (although some medical information may be given by the participant and/or their parents as part of the questionnaires completed during this at-home assessment). At the Week 0 visit and all subsequent visits, the medical history will be reviewed and updated if any changes have occurred.

Self-administered questionnaires will be completed by the participant/parents and the examining physicians. Requests will be made to obtain the participant's relevant medical records, review all previous biopsy materials and radiographic studies, and speak to their primary physician regarding their illness. All clinically meaningful conditions (e.g., inflammatory/autoimmune diseases, metabolic diseases, cardiovascular disease, and renal disease) will be recorded along with onset and resolution dates if applicable. Participants and/or their parents will be asked to identify any exclusionary conditions, such as heart failure, renal impairment, or other renal disease. Participants of reproductive potential will be asked if they are pregnant or breastfeeding.

A registered nurse or physician may take the medical history. A board-certified medical doctor who is licensed to practice medicine will review the medical history.

## **5.2. Medication History and Concomitant Medication**

Participants and/or their parents will be asked about recent and current medication use at the screening visit and at weeks -10, -4, 0, 24, and 62. Between Week 0 and Week 10 most participants will have been inpatients and medication use will already be documented; for those participants who choose to receive treatment on a local outpatient basis during the 10-week treatment period, their medication use will be reviewed weekly. Medication history will include a review of antibiotic use, probiotics, supplements, vitamins, and herbs or non-traditional medications.

After the Week 0 visit, an extensive medication history is not required; rather, any changes that have occurred since the prior study visit will be recorded.

## **5.3. Physical Exam**

Participants will receive a physical examination at all study visits (excluding the Week -4 at-home assessment). The initial physical exam will confirm the participants' dermatomyositis and calcinosis and will help rule out any exclusionary conditions. Exams at all visits will minimally include heart auscultation, lung auscultation, abdominal palpation, skin and joint examination, and muscle strength assessment.

Details of the physical examination procedures are provided in the study's Manual of Procedures (MOP).

## **5.4. Physician Assessment Forms**

As part of their evaluation assessing physicians will complete forms documenting the state of the patient's disease at the time of the visit. One of these forms will be the Physician Calcinosis Activity Visual Analogue Scale. This form will contain directions for the physician on how to score patient calcinosis activity and several ways for them to record this information. This will include a VAS where physicians will mark with a vertical

**Abbreviated Title:** Sodium Thiosulfate (STIC)

**Version Date:** July 07, 2023

line the activity of calcinosis taking into account amount of calcinosis, presence of erythema, consistency of calcinosis, calcinosis warmth, ulceration associated with the calcinosis, texture of the calcinosis, the location of the calcinosis, and any pain associated with the calcinosis. Physicians will also complete the Calcinosis Type and Extent Form. This form records information about the location of a patient's calcinosis and the subtype of calcinosis based on the distribution pattern of the calcinosis. We will also use a Calcinosis Sentinel Lesion form to follow up to 5 calcinosis lesions clinically throughout the study based on assessment by examination, durometry, and photography.

## **5.5. Pregnancy and Breastfeeding Status**

Female participants of reproductive potential will receive a urine or serum pregnancy test at all study visits and during the infusion period of 0 to 10 weeks on a weekly basis, they will also be asked if they are breastfeeding at each of these time points; both are assessed as part of clinical care to eliminate any risks to an unborn fetus or nursing child. The pregnancy tests will be performed at the NIH Clinical Center laboratory.

Any participant found to be pregnant at the screening visit will not be eligible for enrollment until they are no longer pregnant at which time they would undergo a second abbreviated screening visit. Any participant with a positive pregnancy result or who is breastfeeding at the Week -10 visit through Week 10 (during periods of baseline assessments or study treatment administration) will be excluded from enrolling or treatment. Patients found to be pregnant at week 0 will not receive study drug and will complete week 0 assessments that are not contraindicated in the setting of pregnancy. Patients found to be pregnant between weeks 0 and 10 if they have received any study drug will also be asked to return for the week 10, 24 and 62 assessments, again excluding any tests that are contraindicated while pregnant. Patients who are found to be pregnant after week 0 will not receive any additional study drug as long as they remain pregnant. Any patient found to be pregnant prior to week 10 will not be considered a completer for evaluation of the primary outcome. A positive pregnancy result at Weeks 24 or 62 will exclude the participant from undergoing assessments involving ionizing radiation [i.e., dual-energy x-ray absorptiometry (DEXA) and computerized tomography (CT) scans], but will not result in changing their status from being a completer for evaluation.

## **5.6. Muscle Strength and Functional Testing**

Muscle strength and function testing will be administered in this study for research purposes. Details of testing by visit are provided in Table 7 found in Appendix B.

The functional assessment tools including the Health Assessment Questionnaire or Childhood Health Assessment Questionnaire will be given to participants and/or their parents.

Muscle strength and functional assessment will be performed by a physiatrist, as well as physical therapists in the Department of Rehabilitation Medicine, who will administer muscle strength assessment tools. Some additional MMT evaluations may also occur as clinical assessments or as part of other tools that may be performed by a NIEHS physician or practitioner.

**Abbreviated Title:** Sodium Thiosulfate (STIC)

**Version Date:** July 07, 2023

Testing will include the Adult Myopathy Assessment Tool (AMAT) and Childhood Myositis Assessment Score (CMAS), passive range of motion (ROM), sit to stand, 6-minute walk, timed up and go, quantitative muscle testing, Motor Function Measure in neuromuscular disease (MFM), Grip strength, key pinch strength, targeted ROM, Myositis Functional Index version 3 (FI3) and manual muscle testing (MMT).

The AMAT, CMAS and FI3 rate physical function and muscle endurance using timed functional maneuvers and endurance tasks, with higher scores indicating better performance.

For the 6-minute walk assessment, participants will be asked to walk as briskly as is comfortable for them for a 6-minute period on a flat gym surface. Vital signs, including blood pressure, are monitored before, immediately after, and 10 minutes after the test. Distance traveled at specific timed intervals will also be included.

Passive range of motion testing will assess increases in joint range of motion on therapy while minimizing the impact of muscle strength. Full passive ROM will be performed initially, and then on subsequent time points targeted ROM will be performed on hip extension, knee extension, elbow extension, shoulder flexion, shoulder abduction, and the three other joint motions that had the greatest limitation on the initial assessment.

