## 2.1. Outcome Measures

- The primary outcome measure of the study will be greater improvement in calcinosis activity VAS rating from Week 0 to Week 10, compared with any change in calcinosis activity VAS rating observed during the pre-treatment period (from Week -10 to Week 0).

Secondary outcome measures include:

- Greater improvement in quality of life score (CHQ-PF50 for children, SF-36 for adults) from Week 0 to Week 10, compared with any change in quality of life score observed during the pre-treatment period (from Week -10 to Week 0).
- Changes in components of quality of life over time, as measured by quality of life questionnaires (e.g., SF-36, CHQ-PF50, PROMIS, Skindex-29)
- Changes in functional disability over time, measured by CHAQ/HAQ, CMAS/AMAT/Myositis Functional Index, and physical therapy-related assessments (e.g., range of motion, 6-minute walk, timed up and go, sit to stand, Motor Functional Measure (MFM))
- Change in muscle strength over time, measured by manual and quantitative muscle testing

**Abbreviated Title:** Sodium Thiosulfate (STIC)

**Version Date:** July 07, 2023

- Improvement of calcinosis lesions, assessed by Calcinosis Assessment Tool, Sentinel Calcinosis Lesion form, Mawdsley Calcinosis Questionnaire, durometry measurements, photography, and imaging studies
- Changes in gene expression, measured by RNA and protein analyses (e.g., to evaluate changes due to therapy, or differences between responders and non-responders to therapy)
- Incidence and severity of adverse events, including laboratory abnormalities, over time
- Improvement in or stabilization of myositis activity and damage, as assessed by the IMACS core set measures

Secondary outcomes will evaluate for differences in change from week -10 to 0 compared to week 0 to 10 as well as changes at week 24 and 62.

An additional outcome will be validation of the Calcinosis Assessment Tool and the Mawdsley Calcinosis Questionnaire and new imaging modalities for calcinosis, which are under development by our group and associate investigators of the protocol.

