Two-sided paired t-tests will be performed to test for significant differences in the relative percent change in VAS score, absolute percent change in VAS score, and the secondary outcome of change in quality of life score (Physical Function Score of CHQ-PF50 for children, SF-36 for adults) from Week 0 to Week 10, compared with any change in quality of life score observed during the pre-treatment period (from Week -10 to Week 0). The secondary outcomes of changes in the components of quality of life over time, changes in functional disability over time, change in muscle strength over time, and changes in gene expression associated with therapy will also be analyzed using paired t-tests. For the gene expression analysis, multiple testing adjustments will be used to control the false discovery rate. Categorical measures of improvement in calcinosis lesions, improvement in or stabilization of myositis activity, and incidence of adverse events will be analyzed using McNemar tests. Fisher exact tests will be used to test for differences between responders and non-responders to therapy. The severity of adverse events and quantitative measures of improvement in calcinosis lesions and myositis activity will be analyzed using paired t-test or regression to control for additional covariates. Generalized linear mixed models will be considered to analyze quantitative secondary outcomes across time. Descriptive statistics, such as mean, median and standard deviation, of the primary outcome and secondary outcomes of change in VAS, change in quality of life (QOL), change in functional disability, improvement in calcinosis lesions, and change in muscle strength are also of interest and will be used to plan further studies. Prior to statistical testing, the normality of quantitative measures will be evaluated by plotting the empirical distributions of the quantitative measures to look for deviations from normality as well as using QQ-plots. For non-normally distributed endpoints, normalizing transformations, such as the log transformation, will be applied. If normality cannot be achieved by transforming the data, analogous nonparametric tests, such as the Wilcoxon Signed Rank test, will be used in the analysis. The multiple comparison adjustment method that will be used is a stepwise Bonferroni-Class Method as published in Holm (39) and Hochberg (40).

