**Table 7 Schedule of Quality of Life and Myositis Assessments by Study Week**

Assessment	Completed By...	Screening	-10	-4	0	2	4	6	8	10	24	62
CHQ-PF50 (if pediatric) or SF-36 (if adult)	Patient AND Parent of participant (for CHQ); Participant (for SF-36)		X	X	X	X	X	X	X	X	X	X
Physician Calcinosis Visual Analogue Scale	MD	X	X		X	X	X	X	X	X	X	X
Calcinosis Type and Extent Form	MD	X(optional)	X		X			X		X	X	X
Calcinosis Sentinel Lesion Form	MD		X		X			X		X	X	X
IMACS Activity Core Set Measures:												
Physician Global Activity	MD	X	X		X	X	X	X	X	X	X	X
Patient/Parent Global Activity	Participant and parent of participant	X	X	X	X	X	X	X	X	X	X	X
CHAQ (if pediatric) or HAQ (if adult),	Parent of participant and pediatric participant (for CHAQ); Participant (for HAQ)	X	X	X	X	X	X	X	X	X	X	X
Childhood Myositis Assessment Scale (CMAS)	MD	X (optional)	X		X	X	X	X	X	X	X	X
Myositis Disease Activity Assessment Tool (MDAAT)	MD	X	X		X	X	X	X	X	X	X	X
IMACS Disease Damage Core Set Measures:												
Myositis Damage Index (MDI)	MD		X		X	X	X	X	X	X	X	X
Physician Global Assessment of Disease Damage	MD	X	X		X			X		X	X	X
Patient/Parent Global Assessment of Disease Damage	Participant and parent of participant		X	X	X			X		X	X	X

**Abbreviated Title:** Sodium Thiosulfate (STIC)

**Version Date:** July 07, 2023

Assessment	Completed By...	Screening	-10	-4	0	2	4	6	8	10	24	62
IMACS Assessment of Study Outcome Form	MD, Participant, and parent of participant			X a,b	X b			X		X	X	X
Disease Activity Score (DAS)	MD		X		X	X	X	X	X	X	X	X
Calcinosis Assessment Tool (CAT), including Pain VAS	Participant and parent of participant, reviewed by MD, MD	X	X	X a	X	X	X	X	X	X	X	X
Mawdsley Calcinosis Questionnaire	Participant and parent of participant, reviewed by MD, MD		X	X a	X	X	X	X	X	X	X	X
PROMIS® Questionnaire	Participant and parent of participant (pediatric pts)		X	X a	X	X	X	X	X	X	X	X
Skindex-29+3	Participant and parent of participant (pediatric pts)		X	X	X	X	X	X	X	X	X	X
Adult Myopathy Assessment Tool (AMAT)	Rehab Medicine Department		X		X			X		X	X	X
Motor Function Measurement (MFM)	Rehab Medicine Department		X		X			X		X	X	X
Functional Index 3 (FI3)	Rehab [name]		X		X	X	X	X	X	X	X	X
Passive Range of Motion (ROM)	Rehab Medicine Department		X									
Targeted Passive Range of Motion	Rehab Medicine Department				X	X	X	X	X	X	X	X

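### The reading that selects the three most limited joint motions also starts their lead-in change, so reading error shifts that part of the range-of-motion contrast against sodium thiosulfate

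*Combined protocol and SAP*

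**What the plan says.** Section 5.6 gives the purpose: "Passive range of motion testing will assess increases in joint range of motion on therapy while minimizing the impact of muscle strength". It then sets the sequence: "Full passive ROM will be performed initially, and then on subsequent time points targeted ROM will be performed on hip extension, knee extension, elbow extension", followed by shoulder flexion and shoulder abduction, which makes five fixed motions. To these it adds "the three other joint motions that had the greatest limitation on the initial assessment".

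Table 7 (Appendix B) marks full passive range of motion at Week -10 and at no other visit; screening is blank. The row "Targeted Passive Range of Motion" starts at Week 0 and runs through Weeks 2, 4, 6, 8, 10, 24 and 62.

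Section 2.1 places range of motion under the functional-disability secondary outcome, among "physical therapy-related assessments (e.g., range of motion, 6-minute walk, timed up and go, sit to stand" and others. It adds: "Secondary outcomes will evaluate for differences in change from week -10 to 0 compared to week 0 to 10", together with changes at Weeks 24 and 62, for which it names no start value. Section 8.1 says that changes in functional disability "will also be analyzed using paired t-tests".

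Neither 5.6 nor 8.1 provides a second reading before Week 0, a correction for the selection, or separate handling of the selected motions. No range-of-motion summary score is defined.

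**The concern.** One reading does two jobs for the three extra motions: it ranks them as the worst, and it opens their lead-in change. Each reading is the true limitation plus error, and a motion is more likely to be ranked among the worst three when its error makes it look worse. The Week 0 reading carries fresh error, so on average these motions appear to improve between Week -10 and Week 0 with no real change.

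The Week 0 and Week 10 readings play no part in the selection, so the treatment-period change is not distorted. The artefact therefore lies wholly in the lead-in change and is subtracted from any drug effect. A real gain in these motions could be understated or missed. Conversely, if later changes were counted from Week -10, the same artefact would appear as a false gain.

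**Working it through.** **Plan figures.** The documents give no expected effect, reading error or sample-size calculation for range of motion, so there is no stated figure to reproduce. The number of completers, 13, is from 8.3. As a check on the method, the noncentral-t calculation used below returns n = 13 (power 0.911) for Table 3's case of mean difference 10, SD 10 and two-sided alpha 0.05, which matches the plan.

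**Contrast.** For one motion, D = (Y10 - Y0) - (Y0 - Y-10) = Y10 - 2·Y0 + Y-10. With independent reading error of SD σ, the error variance of D is (1 + 4 + 1)σ² = 6σ², and for the mean of m motions it is 6σ²/m.

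**Expected artefact.** With normally distributed readings, the false lead-in gain is (1 - reliability) × the mean deviation of the three worst readings. With 16 candidate motions and reliability 0.90, that deviation is about 1.35 reading SDs, so the gain is 0.10 × 1.35 = 0.135 SD. With error SD 5 and between-motion SD 15, reliability is 225/250 = 0.90 and the reading SD is √250 = 15.8 degrees. The gain is then about 0.134 × 15.8 = 2.1 degrees, as simulated.

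**Simulation with no drug effect and no true change.** Assumptions, none from the documents: 20 candidate motions, true limitation exponential with mean 10 or 20 degrees, three independent readings, and the worst three chosen on the first.

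| Error SD (degrees) | False lead-in gain, mean limitation 10 | False lead-in gain, mean limitation 20 |
|---|---|---|
| 3 | 0.90 | 0.45 |
| 5 | 2.50 | 1.25 |
| 7 | 4.77 | 2.44 |

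The simulated Week 0 to Week 10 change was about 0 throughout. Using 10 or 30 candidates changes these values only modestly. A wider grid under the normal model (8 to 24 candidates, error SD 3 to 8, spread SD 10 to 25) gives 0.3 to 7.8 degrees.

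**Effect on an eight-motion mean** (error SD 5, n = 13, true gain 5 degrees):
- SD of the contrast = √(6 × 25 / 8) = 4.33 degrees.
- Bias = 3/8 × 1.25 = 0.47, or 3/8 × 2.50 = 0.94 degrees.
- Power is 97% with no bias, 93% with bias 0.47 and 87% with bias 0.94.
- With no drug effect, the two-sided rejection rate rises from 5% to about 6.5% or 11%, mainly in the direction of apparent harm.

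**Effect on a three-motion mean**, for comparison: SD = √(6 × 25 / 3) = 7.07 degrees, and power falls from 65% to 42% (bias 1.25) or 22% (bias 2.50).

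Both SDs contain reading error only. Any variation between patients in natural change or response would increase them.

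**The case against.** The strongest reply is about size. Range of motion is one example measure within a secondary outcome. Only three of eight motions are affected, and every input to the calculation is assumed. If contractures are fixed and measurement is precise, the artefact is small. In the lead-in contrast it is conservative and cannot create a false claim of benefit. The plan also looks at Weeks 24 and 62, considers mixed models across time, and records the targeted motions at eight visits from Week 0, so an undistorted change from Week 0 is already available. All of this stands and limits the severity. It does not remove the bias from the contrast that 2.1 specifies.

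A reader might infer more: that power collapses to 22%, or that the trial would often show significant worsening under no effect. Those figures belong to a separate three-motion score, which the plan does not define, and to an SD with no patient-to-patient variation. With a contrast SD of 10, the null rejection rate at a bias of 2.5 degrees is about 13%, against 22% at SD 7.

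A reader might also infer that the most restricted joints are where benefit should show first. The documents do not support this. Section 4.1 describes a high amount of damage in this population, and such joints could equally be the least able to respond.

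A fair objection to the remedy is that change from Week 0 alone gives up the design's only internal control for these motions in an open-label, single-arm study. That is correct, and the reporting must say so.

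**Conclusion.** The point holds in a limited form. Sections 5.6 and 2.1 with Table 7, followed as written, build a bias against sodium thiosulfate into the lead-in contrast for the three selected motions. Mechanism and direction follow from the text, given only that readings contain some error or short-term fluctuation.

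The magnitude is not determinable from the documents; the degree and power figures above are illustrations of scale. How far the bias reaches the reported result also depends on a choice the plan leaves open, namely how the eight motions are combined. Severity is minor: a secondary outcome and a conservative bias, but one that is cheap to remove.

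**What to change.** In 5.6 and 8.1, state that the lead-in versus treatment contrast for range of motion uses the five fixed motions only. Report the three selected motions separately as change from Week 0 to Weeks 10, 24 and 62, labelled descriptive and uncontrolled, and do not use their Week -10 selection reading as a baseline for any change.

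This takes a sentence or two in each section and no new measurement. The cost is that the three selected motions lose their lead-in comparison, and their before-after change cannot by itself be attributed to the drug.

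If the lead-in comparison for these motions is wanted, the alternative is a second, independent reading of them after selection, within the Week -10 visit (expected by 3.1 to last up to about 7 days), used as the lead-in start value. That adds a measurement and helps only patients not yet past that visit.

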## 5.7. Magnetic Resonance Imaging (MRI)

MRI will be administered for research purposes to assess changes in muscle inflammation over the course of the treatment.

Participants without a contraindication will undergo MRI examination of the whole body, which will be conducted in collaboration with the NIH Department of Radiology.

For the MRI scans, a 1.5 Tesla magnet will be used with standardized scanning parameters, including T1, fat-suppressed T2, diffusion weighted images, T2-Map, and STIR images. Scanning time will be 1 hour and will occur as a separate scan then the whole body MRI or MRI/PET. Quantitation of the MRI scans, including T2 and T1 maps, will be developed. For those patients with contractures or other physical limitations stopping them from having MRI performed in the typical position we will make efforts to perform the MRI in a position they can tolerate and that would be reproducible between scans. Research MRI will be performed without gadolinium and without sedation. All efforts possible will be made to make the experience as tolerable as possible, which may include such activities as providing supportive padding, providing blankets during the test, playing the patient music, and any other action that can increase the tolerability for that patient, with the understanding that all options may not be available for all patients.

